5.3.7 Treatment Interruptions and Adverse Event Management Guidelines

In general, the need for treatment interruptions is rare in patients receiving SBRT. Interruptions should be avoided by preventative medical measures and nutritional, psychological, and emotional counseling. Treatment breaks, including indications, must be clearly documented in the treatment record.

Pneumonitis

Radiation pneumonitis is a subacute (weeks to months from treatment) inflammation of the end bronchioles and alveoli. **Note:** It is very important that a Radiation Oncologist participate in the care of the patient, as the clinical picture may be very similar to acute bacterial pneumonia, with fatigue, fever, shortness of breath, nonproductive cough, and a pulmonary infiltrate on chest x-ray. The infiltrate on chest x-ray should include the area treated to high dose, but may extend outside of these regions. The infiltrates may be characteristically "geometric" corresponding to the radiation portal, but may also be ill defined.

Patients reporting symptoms as above will be promptly evaluated and treated. Mild radiation pneumonitis may be treated with nonsteroidal anti-inflammatory agents or steroid inhalers. More significant pneumonitis will be treated with systemic steroids, bronchodilators, and pulmonary toilet. Supra- and concurrent infections should be treated with antibiotics. Consideration of prophylaxis of opportunistic infections should be considered in immunocompromised patients.

It is unlikely that symptomatic pneumonitis will occur during the weeks radiation is actually delivered to the patients. However, if a patient experiences pneumonitis before completing therapy, therapy will be put on hold until symptoms resolve.

When symptomatic pneumonitis resolves to grade 0, the treating physician will contact the RTOG Study Cochair for a decision to continue or terminate protocol therapy. All decisions by the RTOG Co-chair must be documented in the patient's chart.

Bronchial Injury (e.g., bronchial obstruction; bronchial stricture; bronchopleural fistula)

Bronchial injury with subsequent focal collapse of lung may impair overall pulmonary status. It also makes further assessment of tumor response more difficult as the collapsed lung approximates the treated tumor. Because atelectatic lung and tumor have similar imaging characteristics, radiology reports will often describe the overall process as progressive disease while the actual tumor may be stable or shrinking. Investigators are referred to the strict criteria for progressive disease to avoid such mischaracterization.

The consequences of bronchial toxicity, e.g., cough, dyspnea, hypoxia, impairment of pulmonary function test parameters, pleural effusion or pleuritic pain (associated with collapse), will all be graded and reported on adverse event forms.

Chest Wall Pain and/or Fracture (Rib)

When treating lesions about the chest wall, some patients will experience chest wall pain either as a result of intercostal neuropathy or rib fracture. Focal radiation induced osteoporosis can result in both occult and obvious rib fractures generally propagated by severe coughing/sneezing episodes or chest wall trauma (e.g., bumping into a kitchen cabinet). The pain typically occurs several months after treatment and may last several more months.

Changes in Pulmonary Function Tests (e.g., forced expiratory volume (FEV1) decreased; carbon monoxide diffusion capacity (DLCO) decreased; vital capacity abnormal)

Patients enrolled to this study may have some degree of impaired pulmonary function as measured by pulmonary function tests (PFTs), including Forced Expiratory Volume in 1 second (FEV₁), Forced Vital Capacity (FVC), and Diffusing Capacity for Carbon Monoxide (DLCO). The CTCAE Version 4 grading criteria for PFTs assume that all patients have normal baseline pulmonary function. This assumption is not appropriate for this protocol, which is enrolling patients with abnormal baseline function. In order to monitor changes in lung function from baseline, a protocol-specific toxicity classification for PFTs has been developed for use with this study. PFTs will be coded for all patients in both treatment groups using this scale. See RTOG Pulmonary Function Test Toxicity Scale (Section 8.4) for more information.

Other Grade 3 or Higher Adverse Events

All other adverse events Grade 3 or higher, or requiring suspension of therapy, will be reported.

5.3.8 Compliance Criteria

5.3.8.1 Credentialing Compliance

All criteria listed in Credentialing (Section 12) must be completed to the satisfaction of the study team in order to participate in the study. No institution will be allowed to enroll patients without completion of all required credentialing.

5.3.8.2 Dosimetry Compliance

The Image-Guided Therapy Center (ITC) will evaluate dosimetry plans (see Quality Assurance Requirements, Section 5.4). RT treatment plans not meeting the "per protocol" criteria or scored as "variation acceptable" will be classified as "deviation unacceptable." Normal tissue dose constraints are listed above. **NOTE: For the spinal cord, these are absolute limits, and treatment delivery that exceeds these limits will constitute a major protocol violation.** For the non-spinal cord tissues, acceptable deviation allows a maximum point dose no more than 105% of the prescription dose (56.7 Gy or 18.9 Gy per fraction) while fully respecting the defined volume constraint (for serial tissues) OR exceeding the parallel tissue critical volume dose maximum by no more than 5%. Unacceptable deviation exceeds the volume constraint for serial tissues, exceeds the maximum point dose for serial tissues by more than 105% of the prescription dose, or exceeds the parallel tissue critical volume dose maximum by more than 5%.

5.3.8.3 Contouring Compliance

Accurate and appropriate contouring is essential for the generation of dose volume statistics. In addition, it is the desire of ACOSOG and RTOG to compile a comprehensive database of dose volume information coupled with outcomes data (control/toxicity) in order to define accurate dose response effects. As such, we require that the tumor targets, lungs, esophagus, bronchial tree, spinal cord, heart (pericardium), and trachea be contoured in all patients. In addition, any structure listed with a constraint in Critical Structures and residing within 10 cm in any direction from the PTV must be contoured. Appropriateness of contouring will be scored by the study PIs as either no deviation, minor deviation, or major deviation.

5.3.9 SBRT Quality Assurance Documentation

See Quality Assurance Requirements (Section 5.4).

5.4 Quality Assurance Requirements

Surgical quality assurance will be performed by the study chair or designee, as specified below. Brachytherapy and SBRT quality assurance (and credentialing – see Section 12) will be conducted by the Advanced Technology Consortium (ATC), which is a "virtual entity" made up of the following QA centers:

- Image-guided Therapy QA Center (ITC), Washington University in St. Louis
- Radiation Therapy Oncology Group (RTOG) Headquarters Dosimetry Group
- Radiological Physics Center (RPC), M.D. Anderson Cancer Center
- Quality Assurance Review Center (QARC), Lincoln, RI.

5.4.1 Surgery Quality Assurance

All operative and pathology reports will be reviewed by the surgical study chair or designee for success of the resection, as defined in Section 5.1. Problems or concerns about investigator performance will be communicated directly to the investigator by the study chair.

5.4.2 Brachytherapy Quality Assurance

Brachytherapy quality assurance documentation and imaging will be submitted to the Image-guided Therapy QA Center (ITC).

Within two weeks after completion of the post-implant CT scan, submit the following for each patient receiving brachytherapy:

- Baseline diagnostic PET/CT scan (DICOM) of the chest
- Post-implant CT scan (DICOM) at 4 weeks used for treatment planning

- Structure contours (DICOM RT Structure Set) for all structures identified in section 5.2.4
- 3-D CALCULATED dose distributions (DICOM RT Dose) throughout the volume of interest
- Treatment plan information (DICOM RT treatment plan)
- Color isodose images in axial, sagittal, and coronal planes (JPEG or PNG screen captures)
- Color DVH's for the resection margin, 0.5 cm depth (PTV-1), 0.7 cm depth (PTV-2), 1.0 cm depth, and 2.0 cm depth (JPEG or PNG screen captures)
- Online Digital Data Submission Information (DDSI) Form (available at http://atc.wustl.edu/forms/DDSI/ddsi.html username and password required) to report the specified dose parameters (activity/seed, total seeds/strands, total activity, measured strand separation). NOTE: This on-line form will accompany all submissions to ITC.

The required imaging must be submitted digitally in DICOM format. The DICOM files must have the ability to be extracted from the CD. Submission by either CD or SFTP is supported. See QA Submission Instructions (Section 5.4.4).

5.4.3 SBRT Quality Assurance

SBRT quality assurance documentation and imaging also will be submitted to ITC for review.

5.4.3.1 Rapid Review of Treatment Plan for First Patient

Rapid review of the first patient's treatment plan prior to treatment is required for each type of SBRT system used at a site (e.g., Cyberknife, Linac-based, etc.).

The rapid review allows the study team to determine the institution's ability to generate a "per protocol" treatment plan. Each institution must digitally submit the planning CT dataset with the proposed treatment plan prior to the start of treatment for the first patient registered by the institution. The plan will be reviewed centrally by the study co-chair or designee, and suggestions regarding protocol compliance will be forwarded to the participating institution. Once the plan is approved, RTOG Headquarters will notify the site, and treatment may begin.

Prior to the start of SBRT, submit the following materials for the first patient treated with each type of SBRT system used at a site:

- Planning CT dataset (DICOM)
- Structure contours (DICOM RT Structure Set) for critical normal structures, all GTV, CTV, and PTV contours (C1, C3)
- Treatment plan (DICOM RT Plan) for initial and boost beam sets
- 3-D CALCULATED dose distributions (DICOM RT Dose) for initial and boost sets of concurrently treated beams
- Color isodose images in axial, sagittal, and coronal planes (JPEG or PNG screen captures)
- Digital DVH data for all required critical normal structures, GTV, CTV, and PTVs for total dose plan (DV)
- Online Digital Data Submission Information Form (DDSI) (available at http://atc.wustl.edu/forms/ddsi/ddsi.html).

The required imaging must be submitted digitally as DICOM RT. Submission by either CD or SFTP is supported. See QA Submission Instructions (Section 5.4.4).

5.4.3.2 Treatment Plan Review for Subsequent Patients

Only the first patient's treatment plan for each system used at each site will be reviewed prior to treatment. For all subsequent patients, the study co-chair or designee will perform retrospective treatment plan review after complete data for the first 50 cases enrolled have been received at ITC. Subsequent reviews will be performed for every 50 patients enrolled and treated with SBRT thereafter.

Required Materials for Subsequent Patients

Within four weeks after completion of SBRT, submit the required materials identified in Section 5.4.3.1 for all patients.

The required imaging must be submitted digitally as DICOM RT. Submission by either CD or SFTP is supported. See QA Submission Instructions (Section 5.4.4).

5.4.3.3 Final Dosimetry Data Submission for All Patients

Within four weeks after completion of SBRT, submit hard copies of the following for all patients:

- Radiotherapy Form (T1) (available on the Z4099 page of http://www.acosog.org)
- Daily radiation treatment record from patient's medical chart

Hard copies of the T1 form and treatment records will be submitted to ITC. See QA Submission Instructions (Section 5.4.4).

5.4.4 QA Submission Instructions

All CT planning and treatment information (e.g., post-implant CT files, dose files, plan files, and structure files) must be submitted digitally in DICOM RT format. Submission by either CD or SFTP is supported. Multiple studies for the same patient may be submitted on one CD; however, submit only one patient per CD.

All submissions via CD or hard copy should be sent to:

Image-guided Therapy QA Center [name] [contact] [contact] Email: [contact]

A Secure FTP (SFTP) account with username and password can be obtained by contacting the ITC at [contact] or [contact]. Guidelines for digital submission are available at http://atc.wustl.edu.

Sites must notify ITC via e-mail when digital data are submitted. The e-mail must include the study and patient identification numbers and a description of the datasets being submitted (e.g., brachytherapy QA, SBRT treatment plan, etc.).

NOTE: If brachytherapy or SBRT data cannot be submitted, the ITC must be notified. The notification must be submitted in writing via email to [contact].

5.5 Systemic Therapy

Patients with clinical or pathological Stage Ia or Ib should not be offered chemotherapy, as eligible patients per staging should have tumors ≤ 3 cm.

Patients found at surgery to have pathological Stages Ib (> 3 cm), IIa, IIb and IIIa may be offered adjuvant chemotherapy at the discretion of the treating physician.

The regimen chosen will be at the discretion of the treating physician. Any adjuvant chemotherapy administered to the patient must be documented in the patient's hospital/clinic chart.

5.6 Early Discontinuation of Protocol Therapy

Protocol therapy may be discontinued early at the discretion of the investigator for the following reasons:

- Excessive or unacceptable toxicity
- Patient refusal or withdrawal of consent for treatment
- Disease relapse/progression during therapy

Patients who discontinue treatment early should be followed as described in Follow-up (Section 6).

6 Follow-up

After completion of protocol therapy, patients will be monitored for relapse/progression and survival for five years as required by the Study Calendar.

6.1 Follow-up of Patients Who Do Not Receive Protocol Treatment

Registered patients who do not receive protocol therapy will be followed as required by the Study Calendar.

6.2 Follow-up of Patients with Disease Relapse/Progression

Patients with local, regional or distant disease relapse/progression during or after protocol therapy will be followed for survival and quality of life, as required by the Study Calendar. Patients may be treated at the physician's discretion. NOTE: If resection is attempted after disease relapse/progression, submit operative and pathology reports and 4-week post-surgery adverse event data.

6.3 Follow-up of Patients Who Discontinue Treatment Early for Reasons Other Than Disease Relapse/Progression

Patients who discontinue protocol therapy for reasons other than disease relapse/progression will be followed as required by the Study Calendar.

7 Evaluation of Outcomes

All patients will be followed for 5 years for survival and disease relapse/progression. Adverse events including surgical morbidity and mortality and late radiation effects also will be monitored. Quality of life will be evaluated for patients who have consented to participate in that portion of the study.

7.1 Response to SBRT (Arm 2)

Response to SBRT will be assessed and reported according to RECIST Version 1.1 criteria.

Evaluation of Target Lesions (Primary Tumor)

- **Complete Response (CR)**: Disappearance of all target lesions. Any pathological lymph nodes (whether target or non-target) must have reduction in short axis to <10 mm.
- **Partial Response (PR)**: At least a 30% decrease in the sum of the diameters of target lesions, taking as reference the baseline sum diameters.
- **Progressive Disease (PD)**: At least a 20% increase in the sum of the diameters of target lesions, taking as reference the smallest sum on study (this includes the baseline sum if that is the smallest on study). In addition to the relative increase of 20%, the sum must also demonstrate an absolute increase of at least 5 mm. (Note: the appearance of one or more new lesions is also considered progression).
- **Stable Disease (SD)**: Neither sufficient shrinkage to qualify for PR nor sufficient increase to qualify for PD, taking as reference the smallest sum diameters while on study.

7.2 Relapse/Progression Definitions

All patients will be assessed for disease relapse/progression. The types of local, regional and distant relapse/progression will be recorded to determine if there are differences in the pattern of relapse/progression between arms.

PET/CT is required to confirm disease relapse/progression (i.e., if CT scan alone is suspicious for relapse/progression, then PET/CT is required to confirm disease status). Biopsy confirmation of relapse is highly recommended but not required. When biopsy is feasible, the following methods are recommended: fine-needle aspiration biopsy, EBUS, EUS, VATS or open biopsy.

CT imaging at three months will be considered the new baseline to account for inflammatory changes and fibrosis after SBRT or SR. The table below describes the different areas defined as local, regional, and distant relapse/progression after treatment effects have subsided.

Type of Recurrence	Modality	Description (after treatment effects have subsided)		
Local Failure				
Primary tumor failure (PTF)	SBRT	Appearance of residual tumor located within the extent of the primary targeted tumor.		
Marginal failure (MF)	SR/SBRT	SR: Appearance of tumor ≤ 2 cm in any direction of the staple-line or the structures immediately adjacent to prior tumor site (chest wall/ mediastinum/ diaphragm/ spine).		
		SBRT: Appearance of tumor ≤ 2 cm in any direction of the primary tumor or structures immediately adjacent to primary tumor (lung/ chest wall, mediastinum/ diaphragm/ spine).		
Involved Lobe failure (ILF)	SR/SBRT	SR: Appearance of tumor > 2 cm in any direction of the staple-line.		
		SBRT: Appearance of tumor > 2 cm in any direction of the primary tumor.		
Port site/wound failure (PWF)	SR	Appearance of tumor at a port or incision site after VATS or open resection.		
Regional Failure				
Non-primary lobe failure (NLF)	SR/SBRT	Appearance of tumor within another ipsilateral (non- primary) lobe.		
Hilar nodal failure (HNF)	SR/SBRT	Appearance of tumor in ipsilateral hilar lymph nodes		
Ipsilateral mediastinal nodal failure (MNF)	SR/SBRT	Appearance of tumor in ipsilateral mediastinal and/or subcarinal lymph nodes.		
Distant Failure				
Distant nodal failure (DNF)	SR/SBRT	Appearance of tumor in ipsilateral supraclavicular or contralateral lymph nodes .		
Distant metastatic failure (DMF)	SR/SBRT	Appearance of tumor deposits characteristic of NSCLC metatstasis (chest wall other than incision sites or immediately adjacent to primary, mediastinal structures/diaphragm, malignant pleural effusion/pericarial effusion), contralateral lung and/or other distant sites.		

Categories of Relapse/Progression

7.3 Documentation of Relapse/Progression

Submission of the biopsy pathology report (if available) and scan reports at the time of relapse/progression is required for all patients. See the Schedule of Forms.

7.3.1 Central Review of Imaging at Relapse/Progression

Submission of imaging to document disease relapse/progression is required in the absence of a tissue diagnosis. Imaging also may be requested by the study team for confirmation of reported relapse/progression on a case-by-case basis. Within 1 month after the request is received by the site, electronic copies of the imaging should be sent to the ITC. The following imaging and reports are required:

- Images from the CT scan done at 3 months post-treatment
- Images from the CT scan and PET/CT scan done at the time of relapse/progression
- Copies of the corresponding radiology reports
- Online Digital Data Submission Information Form (DDSI) (available at http://atc.wustl.edu/forms/ddsi/ddsi.html).

All materials must be submitted to:

Image-guided Therapy QA Center [name] [contact] [contact] Email: [contact]

The retrospective central review may be conducted electronically via the internet, so imaging must be submitted digitally in DICOM format. The digital files may be burned to a CD and mailed to ITC. Multiple studies for the same patient may be submitted on one CD; however, submit only one patient per CD. Alternative electronic methods (e.g., sFTP) are possible. Contact ITC for more information.

8 Adverse Event Reporting

The prompt reporting of adverse events is the responsibility of each investigator engaged in clinical research, as required by Federal Regulations. Toxicities/adverse events must be described and graded using the terminology and grading categories defined in the NCI's Common Toxicity Criteria (CTCAE). Version 4.0 (except changes **PFTs** Section 8.4). The CTCAE available in see is at http://ctep.cancer.gov/reporting/ctc.html. Attribution to protocol treatment for each adverse event must be determined by the investigator and reported on the required forms, using the codes provided.

8.1 Routine Adverse Event Reporting

All expected or unexpected adverse events, regardless of grade or treatment attribution, must be recorded on AE case report forms (CRFs).

Some serious adverse events may require expedited reporting using the AdEERS reporting system, as defined below. **NOTE: All AEs including those submitted to NCI via the Adverse Event Expedited Reporting System (AdEERS) must be recorded on the AE CRF.** Expedited reporting is in addition to and does not supplant the reporting of AEs as part of the data submission requirements for the study.

8.2 Expedited Adverse Event Reporting

An expedited AE report is submitted via the AdEERS web application. Assistance for using AdEERS or for completion of the AdEERS templates is available at http://ctep.cancer.gov/.

What to Report

AdEERS Reporting Requirements for Adverse Event	s that Occur within 30 Days ¹ of the F	End Date of
Non-investigational Treatment on Phase III Trials		

Phase III Trials										
	Grade 1	Grade 2	Grade 3	Grade 4		Grade 5				
	Unexpected and Expected	Unexpected and Expected	Unexpected and Expected	Unexpected	Expected	Unexpected	Expected			
Unrelated Unlikely	Not Required	Not Required	Not Required	Not Required	Not Required	10 Calendar Days	10 Calendar Days			
Possible Probable Definite	Not Required	Not Required	Not Required	10 Calendar Days	Not Required	10 Calendar Days	10 Calendar Days			
 1 Adverse events with attribution of possible, probable, or definite that occur greater than 30 days after the last dose of treatment (surgery or radiation) require reporting as follows: AdEERS 10 calendar day report: 										

• Grade 4 and Grade 5 unexpected events

How to Report

AdEERS reports are submitted electronically via the AdEERS web application.

The AdEERS application is available at: http://ctep.cancer.gov/reporting/adeers.html.

Where to Report

For electronic submission: Use the AdEERS web application.

Secondary Malignancies

All cases of acute myeloid leukemia (AML) and myelodysplastic syndrome (MDS) that occur in patients on NCI-sponsored trials following treatment for cancer will be reported via the AdEERS web application within 30 days of an AML/MDS diagnosis.

IRB Submission

All local AdEERS reports must be submitted to your Institutional Review Board (IRB) within 90 days of knowledge and reporting of the event. You should follow your IRB's policies and procedures in submitting external adverse events and safety reports.

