There have not been any prospective, randomized trials to compare the efficacy or the toxicity profile of SR to SBRT in high risk patients. Currently, it is difficult to make comparisons between the therapies for several reasons: 1) There may be some selection bias with less healthy patients being treated with SBRT, potentially confounding efficacy determinations. 2) Most surgical studies that have been published on SR have not used Common Toxicity Criteria for reporting morbidity. This may lead to over-reporting of complications. For instance a common post-operative complication after thoracic surgery is atrial fibrillation. However in most cases this would be a grade 2 complication and only be classified as grade 3 if the atrial fibrillation was incompletely controlled medically or required a device for control. 3) Most surgical series will only report 30-day mortality, and rarely mortality occurring at longer follow-up. A recent report of SBRT demonstrated a 7.14% incidence of grade 5 toxicity, with most deaths occurring many months or years after treatment was completed [8]. In this same study of 70 patients there were 7 (10%) grade 3 or 4 toxicities. A large study of 182 patients undergoing segmental resection demonstrated complications in 59 (32.4%) of patients of which 24 (13.2%) were considered major [103]. It is unclear for the reasons stated above how many complications would have been graded as 3 or higher. This randomized study will allow us to make comparisons in a homogenous patient group. The Charleson Co-morbidity Index can be used to characterize general health between comparison groups, providing a risk-profile.

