8.3.4 Stereotactic Body Radiation Therapy

Pneumonitis, atelectasis, bronchial obstruction, bronchial stricture, bronchopleural fistula, chest wall pain, fracture, changes in pulmonary function tests (e.g., forced expiratory volume (FEV1) decreased; carbon monoxide diffusion capacity (DLCO) decreased; vital capacity abnormal), pulmonary fibrosis, burn, dermatitis radiation, alopecia, cough (may be productive), dyspnea, fever, fatigue, pericarditis, pericardial effusion, chest pain – cardiac, palpitations, heart failure, myocardial infarction, paresthesias, generalized muscle weakness, esophagitis, dysphagia, aortic or arterial injury, hemoptysis, pain of skin.

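### After day 30, a treatment-attributed death from a listed (expected) toxicity needs no expedited report in either arm, and the gap is likely to fall mainly on SBRT

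*Combined protocol and SAP*

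**What the plan says.** The table in section 8.2 sets one rule for events within 30 days of the end of treatment and another for later ones.

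- **Within 30 days.** All four grade 5 cells (expected or unexpected, attributed or not) read "10 Calendar Days".
- **After 30 days.** Footnote 1 covers "Adverse events with attribution of possible, probable, or definite that occur greater than 30 days after the last dose of treatment (surgery or radiation" (the quotation stops inside a bracket naming both treatments). The events that then need a 10-day report are "Grade 4 and Grade 5 unexpected events". Expected grade 5 events are not mentioned.

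Section 8.3.4 gives the expected events for SBRT without any grade limit. It begins "Pneumonitis, atelectasis, bronchial obstruction, bronchial stricture, bronchopleural fistula, chest wall pain, fracture" and goes on to "pericarditis, pericardial effusion, chest pain – cardiac, palpitations, heart failure, myocardial infarction" and "aortic or arterial injury, hemoptysis, pain of skin". Section 8.3.1 gives the corresponding list for surgery.

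On timing, section 5.3.7 says: "Radiation pneumonitis is a subacute (weeks to months from treatment) inflammation of the end bronchioles and alveoli". Section 1.1 cites an SBRT series with 7.14% grade 5 toxicity, "with most deaths occurring many months or years after treatment was completed". The same paragraph criticises surgical series for seldom reporting mortality beyond 30 days.

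**The concern.** The reporting duty drops sharply at day 30. A death that has nothing to do with treatment is expedited on day 29, while a death definitely caused by treatment may not be on day 31. The protocol gives no reason for this, and its own account of SBRT toxicity puts the harm on the far side of the line.

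What is at stake is the speed of causal information about fatal toxicity. If a planning or delivery problem caused several late deaths from listed toxicities, no individual 10-day report would be required. Section 8.2 also ties its stated IRB submission to AdEERS reports, so that route would not be triggered either. The other safeguards are slower or aimed elsewhere. The one formal interim analysis (section 10.3.2) tests survival futility at 79 deaths. After the first plan for each SBRT system at a site, plans are reviewed retrospectively in batches of 50 (section 5.4.3.2). Section 10.1.1 defends the 10-point survival margin by the better adverse event profile expected of SBRT, so late toxic deaths bear on the design rationale as well.

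**Working it through.** **Step 1: apply the rule to example deaths.** These are constructed cases, read against sections 8.2, 8.3.1 and 8.3.4, taking a listed term as expected at any grade.

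| Death | Attribution | On that arm's expected list? | 10-day report? |
|---|---|---|---|
| Surgery, day 10 | any | either | yes |
| SBRT, day 20 | any | either | yes |
| SBRT, month 4, pneumonitis | definite | yes | **no** |
| Surgery, day 45, sepsis | definite | yes | **no** |
| SBRT, month 4, sepsis | possible or stronger | no | yes |

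The gap is thus defined by three conditions: later than 30 days, attributed to treatment, and a listed event. Arm is not one of them.

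**Step 2: where the deaths fall, on the protocol's own figures.**

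*SBRT.* The cited series has 70 patients (section 1.1). 5/70 = 7.14%, which reproduces the stated rate; 4/70 = 5.71% and 6/70 = 8.57% do not. The exact 95% interval is 2.36% to 15.89%. For 200 patients per arm (section 10.2), 200 × 5/70 = 14.3, with an interval of 4.7 to 31.8. Most of those deaths were late. The rate is probably too high for this trial: the series treated central tumors, which had more toxic deaths (section 1.1), and section 2.1 excludes them.

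The documents give no late toxic death rate for peripheral tumors, so I assume a range:

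| Assumed rate | Expected per 200 | P(at least one) = 1 − (1 − p)^200 |
|---|---|---|
| 1% | 2 | 87% |
| 2% | 4 | 98% |
| 4% | 8 | over 99.9% |

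*Surgery.* The Z4032 table in section 1.1 gives 30-day deaths of 1/114 = 0.88% and 2/109 = 1.83%, matching its 0.9% and 1.8%. Pooled, 3/223 = 1.35%, or 2.7 per 200 (exact 95% interval 0.6 to 7.8). All fall inside the window and would be expedited. The documents give no comparable figure for treatment-related surgical deaths after 30 days.

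**Step 3: what a slower channel means in patients treated.** Accrual is projected at 6 to 10 per month (section 1.4.1). With equal arms that is 3 to 5 SBRT patients per month. CDUS submission is quarterly (section 11.6) and the study chair and statistician review twice a year (section 10.4).

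- Shortest wait, slowest accrual: 3 months × 3 = 9 patients.
- Longest wait, fastest accrual: 6 months × 5 = 30 patients.

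This applies only while the trial is accruing.

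**The case against.** The strongest reply is that nothing is lost, only not expedited. Section 8.1 requires every adverse event on the case report form, whatever its grade or attribution. Section 5.3.7 says other events of grade 3 or higher will be reported. Death is the primary endpoint. CDUS data go to CTEP quarterly, the Data Monitoring Committee oversees the trial, and the study team watches for severe adverse effects. The table is headed for non-investigational treatment, is coherent on its own terms, and touches no endpoint or analysis.

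Most of that stands, and it rules out several stronger readings that a reader might take from section 8.2:

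- *Late SBRT deaths never trigger a report.* They do; what is missing is the expedited report and the IRB submission tied to it.
- *The surgical arm is fully covered.* Footnote 1 treats both arms alike, and a late surgical death from a listed event is equally exempt.
- *Almost no late SBRT death would be expedited.* The documents do not give the causes of death in the cited series. Sepsis, lung infection, adult respiratory distress syndrome and thromboembolic events are on the surgery list but not on the SBRT list. If attributed to SBRT, they would be expedited after day 30; after surgery they would not.
- *A cluster would surface only at the half-yearly review.* Quarterly CDUS submission contradicts this.

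It is also fair to object that the protocol never says whether *expected* takes severity into account. If it does, a fatal case of a listed event might count as unexpected and be reportable. Nothing in section 8 says so, and section 8.4 suggests otherwise: it makes death grade 5 on the pulmonary function scale, while changes in pulmonary function are on both expected lists. At best, two sites could classify the same death differently.

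What the reply does not answer is the gap itself. None of the other channels is a causal report due within 10 days. As far as the study calendar can be read, scheduled adverse event assessment also ends at 12 months, so routine attribution data are weakest for the latest deaths.

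**Conclusion.** The concern holds as a gap in the expedited rule, not as a failure to record deaths and not as a bias written into one arm. After day 30, an attributed death from a listed event needs no 10-day report in either arm. That this falls mainly on SBRT is an inference from timing. It rests on the cited series, on section 5.3.7, and on the assumption that a meaningful share of late SBRT deaths would come from listed toxicities.

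The number of deaths affected is uncertain: 2 to 8 per 200 SBRT patients at assumed rates of 1% to 4%, and about 14 (95% interval about 5 to 32) at 7.14%. The 14 is a point estimate, not a ceiling, and is probably high for peripheral tumors. It also counts all toxic deaths, including any that were early or from unlisted causes and so already reportable. The primary analysis is unaffected. The point is an inexpensive safety improvement that the sponsor should make.

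**What to change.** Amend footnote 1 to the section 8.2 table so that, beyond 30 days and throughout follow-up, a 10-day report is required in both arms for:

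- unexpected grade 4 events with possible, probable or definite attribution (as now); and
- all grade 5 events with possible, probable or definite attribution, whether expected or unexpected.

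Copy these reports to the Data Monitoring Committee. For deaths, this also removes any dependence on whether *expected* takes severity into account.

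The cost is a line of protocol text and a small number of further reports: the SBRT counts given above, plus any late attributed surgical deaths, which the documents do not allow me to estimate.
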